## **7.2 Secondary Endpoints**

### **Safety and Tolerability**

Safety analysis will be conducted on all patients that received at least one dose of PD-0332991 during the study period or follow-up. An adverse event is any unfavorable and unintended sign, symptom, syndrome or illness that develops during the period of observation in the clinical study, including a new illness or condition, worsening of a concomitant illnesses or condition, effect of the study medication or combination of 2 or more factors. Causal relationships are not addressed in this nomenclature. Adverse events will be collected from the time the subject signs the informed consent form throughout the period of follow-up.

### **Overall Survival**

Overall survival (OS) is measured from the entry onto a trial until death of any cause. Date and cause of death will be recorded. The cause of death will be categorized as either cancer-related or cancer-unrelated.

### **Overall Response Rate**

The best overall response is the best response recorded from the start of treatment until disease progression or recurrence. The objective response rate (ORR) is the proportion of subjects with either a confirmed CR or a confirmed PR as determined using modified RECIST (Version 1.1) criteria, as evaluated by the Investigator. A confirmed CR or PR requires repeat assessments no less than 28 days after the response criteria are first met. Subjects who have not met this criteria for response will be considered non-responders. As the clinical relevance of stable disease (SD) may be important in HCC, subjects with the response of SD will be recorded and documented. Disease control rate defined as CR + PR +SD will be calculated for all subjects treated with PD-0332991.

## 8.0 Drug Information

### 8.1 General

PD-0332991 (molecular weight: 573.67 g/mol) is a highly selective, reversible inhibitor of cyclin-dependent kinases (Cdk) 4 and 6 that is being studied for use in the treatment of cancer. Inhibition of Cdk4/6 blocks DNA synthesis by prohibiting the progression of the cell cycle from G1 to S-phase. Thus, PD-0332991 functions as a cytostatic agent.

PD-0332991 is delivered as an oral capsule that is packaged and stored at 15-25°C.

### 8.2 Clinical Pharmacology

#### Pharmacokinetics and Metabolism of PD-0332991

As of March 1, 2008, three studies evaluating the safety, efficacy, pharmacodynamics and PK of PD-0332991 have started. Preliminary PK parameters are available from 73 subjects following a single-dose (Day 1) and 51 subjects at steady-state (Day 8) following administration of daily doses ranging from 25 to 225 mg of PD-0332991. Peak serum concentrations varied from 10-104 ng/mL (Day 1) and 16-186 ng/mL (Day 8) with escalating PD-0332991 dose, and time to peak concentration was 4-7 hours (Day 1) and 3-7 hours (Day 8). Mean estimates of the pharmacokinetic parameters after oral administration of 200 mg of PD-0332991 at steady-state (Day 14 of Cycle 1) were 155 ng/mL peak serum concentration at 4 hours after dosing and effective plasma  $t_{1/2}$  ~32 hours.

#### Absorption and Elimination of PD-0332991

A pilot food effect assessment was conducted in 12 subjects following administration of either 125 mg or 200 mg doses of PD-0332991. For the fed state, subjects completed an 800-1000 calorie meal (at least 50% of which was from fat). The fasted condition was a 10-hour overnight fast. In general, no change in rate of absorption (median  $T_{max}$  = 7, range 4-24 hours) was observed between the fed and fasted state. Higher exposures and peak concentrations were observed in the fed state compared to the fasted state, but these were not considered to be clinically significant as the mean % increase in exposure was less than 25%. Thus, PD-0332991 can be administered without regard to food.

Renal excretion of PD-0332991 was determined to be a minor route of elimination in humans (1.4% of unchanged drug in the urine; clearance rate = 6373 mL/hr).

### 8.3 Dispensing PD-0332991

PD-0332991 will be dispensed via the Jefferson Medical Oncology outpatient offices.

### 8.4 Rationale for Dose and Regimen

A single agent Phase I study in advanced cancer (N=74) determined the recommended Phase II dose for the Schedule 3/1 (3 weeks on and 1 week off, cycling) and Schedule 2/1 (2 weeks on and 1 week off, cycling) to be 125 mg/d and 200 mg/d, respectively. Two additional studies using the Schedule 3/1 are ongoing at Pfizer. For this study, Schedule 3/1 will be utilized unless adverse events require dose modifications as described below (**Table 8.1**).

**Table 8.1** Dose Modification Levels for PD0332991

Dose Level	Daily oral dose	Number of tablets	
		100 mg	25 mg
	per day x 21d, 1 w off		
Standard Dose	125 mg	1	1
Dose Reduced – 1	100 mg	1	0
Dose Reduced – 2	75 mg	0	3

**Table 8.1** outlines the recommended dose reductions for bone marrow toxicity due to PD-0332991.

Study eligible subjects potentially may have baseline myelosuppression due to their underlying liver disease or hypersplenism that is equivalent, according CTCAE v 4 scale to Grade 1 leucopenia, neutropenia and thrombocytopenia and Grade 2 anemia. For example, subjects are eligible to be enrolled on this study with:

- Hemoglobin  $\geq$  8.0 g/dl (CTCAE v 4 Grade 2)
- WBC  $\geq$  4,000/uL (CTCAE v 4 Grade 1)
- Absolute neutrophil count  $\geq$  1,500/uL (CTCAE v 4 Grade 1)
- Platelets  $\geq$  75,000/uL ((CTCAE v 4 Grade 1)

See **Table 8.2** for definitions and **4.1 Eligibility Inclusion Criteria**.

**Table 8.2** Standard CTCAE v 4 scale

Adverse Event	0	1	2	3	4
Hemoglobin (Hgb)	WNL	< LLN - 10.0 g/dl	8 - < 10 g/dl	6.5 - < 8 g/dl	< 6.5 g/dl or life threatening
WBC	WNL	< LLN - 3.0 x 10  /L	$\geq$ 2.0 - < 3.0 x 10  /L	$\geq$ 1.0 - < 2.0 x 10  /L	< 1.0 x 10  /L
ANC	WNL	< LLN – 1.5 x 10  /L	$\geq$ 1.0 - < 1.5 x 10  /L	$\geq$ 0.5 - < 1.0 x 10  /L	< 0.5 x 10  /L
Platelets	WNL	< LLN - 75 x 10  /L	$\geq$ 50.0 - < 75.0 x 10  /L	$\geq$ 25 - < 50.0 x 10  /L	< 25 x 10  /L

If a subject is not able to tolerate the 75 mg dose, then treatment should be discontinued. If a dose reduction has been performed, the subject may be re-escalated by the treating physician provided toxicities have resolved to Grade 2.

**Table 8.3** outlines the procedures for dose modifications for bone marrow toxicity related to PD0332991.

Due to baseline coagulopathy and tendency to have bleeding events due to underlying liver disease, dose modifications should not be based on hemoglobin values. If a subject experiences bone marrow toxicity of both WBCs and platelets the recommended dose adjustment should be based on WBC count. It is recommended that standard of care be followed for administration of RBCs and platelets and for vitamin K in patients with ESLD.

**Table 8.3** Dose modifications/delays for bone marrow toxicity related to PD0332991

Grade of Event CTCAE v 4.03	Dose Interruption	Dose Modification for Remainder of Cycle.	Dose Modification for Subsequent Cycles
0-2	Treat on time	No change	No change
3-4	
 
• Delay until <math>\leq</math> Grade 2
 
• Administer 6 mg pegfilgrastim (Neulasta) subcut if WBC/ANC does not recover to <math>\leq</math> Grade 2 after 1 week dose interruption
 
	
 
• First episode: No change
 
• Second episode within cycle after co-administration with pegfilgrastim: Reduce 1 dose level
 
	
 
• Continue at dose level from previous cycle
 
• If serious drug-related myelosuppression occurs including: A. febrile neutropenia or B. sepsis with neutropenia, in previous cycle institute permanent dose reduction at -1 dose level
 
• If bone marrow toxicity recurs at <math>\geq</math> Grade 3 with leucocyte growth factor administration then
 

			institute permanent dose reduction at -1 dose level 
 
• If unable to resume PD-0332991 due to BM toxicity for an entire cycle, institute permanent dose reduction at -1 dose level
 
• If bone marrow toxicity remains at <math>\leq</math> Grade 2 for remainder of a previous cycle after administration of pegfilgrastim, then administer with subsequent cycles, 6 mg subcut on day 1 once per cycle
 

--	--	--	---

Note: if a subject does not have insurance coverage for pegfilgrastim it is permissible to substitute filgrastim (Neupogen) 5 mcg/kg, rounded up to nearest vial size, subcut daily x 3 days.

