### **5.3 Visit 3 – Toxicity Assessment**

Initial safety and tolerability of the study drug will be assessed after 2 weeks on PD-0332991. The evaluation will include:

1. Clinical assessment – including interval history, physical examination, weight, vital signs, signs/symptoms, and performance status.
2. Toxicity assessment. Adverse events will be graded using the National Cancer Institute (NCI) Common Toxicity Terminology Criteria for Adverse Events v 4.0 (CTCAE v 4.0).
3. Concomitant medication review
4. Blood cell counts (CBC with differential, platelets) and comprehensive chemistries (albumin, alkaline phosphatase, total protein, BUN, creatinine, AST (SGOT), ALT (SGPT), total bilirubin, calcium, sodium, potassium, chloride, bicarbonate), lactate dehydrogenase (LDH).

If subject experiences a Grade 3 or greater toxicity deemed related to study drug, PD-0332991 will be temporarily discontinued. After the resolution of toxicity to Grade 2 or less, PD-0332991 will be restarted at the initial dose. The study treatment will be continued until disease progression or unacceptable side effects (Grade 3 or greater). Subjects with unacceptable side effects (Grade 3 or greater) for a second time on PD-0332991 will be removed from the study. The only exception to this are: Grade 3 anorexia, nausea vomiting, stomatitis/mucositis or diarrhea that will lead to investigational product withdrawal only if not manageable despite maximum supportive care.

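### Rules for Grade 3-4 marrow toxicity conflict: 5.3 and 9.13 restart at 125 mg and remove the patient at a second event, while Table 8.3 keeps the patient on treatment, at a reduced dose under named triggers

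*Combined protocol and SAP*

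**What the plan says.** Two sets of rules cover the same events.

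**Section 8.4.** Table 8.1 "outlines the recommended dose reductions for bone marrow toxicity due to PD-0332991": 125 mg, then 100 mg, then 75 mg. For Grade 3-4 marrow toxicity, Table 8.3 holds the drug until Grade 2 or less. A first episode leaves the dose unchanged for the rest of that cycle. The other entry for the current cycle is "Second episode within cycle after co-administration with pegfilgrastim: Reduce 1 dose level".

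For subsequent cycles the default is the previous cycle's dose level. Three situations call instead for a permanent reduction:
- febrile neutropenia, or "sepsis with neutropenia, in previous cycle institute permanent dose reduction at -1 dose level";
- recurrence at Grade 3 or above with growth factor;
- "If unable to resume PD-0332991 due to BM toxicity for an entire cycle, institute permanent dose reduction at -1 dose level".

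The text before the table stops treatment if 75 mg is not tolerated. It then adds: "If a dose reduction has been performed, the subject may be re-escalated by the treating physician provided toxicities have resolved to Grade 2".

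**Sections 5.3 and 9.13.** After a related toxicity of Grade 3 or greater, 5.3 says "After the resolution of toxicity to Grade 2 or less, PD-0332991 will be restarted at the initial dose". Section 9.13 gives the same restart dose but asks for Grade 1 or less. On recurrence, 5.3 says "Subjects with unacceptable side effects (Grade 3 or greater) for a second time on PD-0332991 will be removed from the study", and 9.13 matches it. Both then limit the escape from removal: "The only exception to this are: Grade 3 anorexia, nausea vomiting, stomatitis/mucositis or diarrhea", where withdrawal follows only if supportive care fails. The heading of 9.13 names hematological as well as non-hematological events.

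**The concern.** Myelosuppression is the drug's principal dose-limiting toxicity (section 1.2). All eleven dose-limiting toxicities reported in section 9.10 were neutropenia, thrombocytopenia or both. The protocol also admits patients with baseline Grade 1 cytopenias (section 8.4). These are therefore rules the site should expect to use.

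At a repeat Grade 3-4 marrow event, one section tells the investigator to take the patient off study and another to continue. After neutropenic sepsis, one section fixes a lower dose for later cycles and two others name the full dose. A treating physician who follows any one of these sections in good faith breaches another.

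**Working it through.** The plan states no figure to reproduce. The check is a comparison of the rules, plus the dose arithmetic.

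**Inputs.** Dose levels of 125, 100 and 75 mg for 21 days (Table 8.1); hold, reduction and continuation rules (Table 8.3 and the text before it); restart and removal rules (5.3, 9.13); grade limits (Table 8.2). The patient starts at 125 mg and the event is judged related.

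| Situation | Table 8.3 and 8.4 | 5.3 | 9.13 |
|---|---|---|---|
| First episode, restart in the same cycle | 125 mg at Grade 2 or less | 125 mg at Grade 2 or less | 125 mg at Grade 1 or less |
| First event is febrile neutropenia or neutropenic sepsis: later cycles | 100 mg, permanent | 125 mg | 125 mg |
| First event, whole cycle missed: next treated cycle | 100 mg, permanent | 125 mg | 125 mg |
| Repeat event, second episode in a cycle after pegfilgrastim | one level lower | removed | removed |
| Repeat event, recurrence with growth factor | permanent reduction | removed | removed |
| Repeat event that is febrile neutropenia or neutropenic sepsis, or costs a whole cycle | permanent reduction | removed | removed |
| Repeat event, none of these triggers | previous cycle's dose | removed | removed |

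**Repeat event.** The two schemes disagree in every repeat-event row. Table 8.3 orders reductions only for Grade 3-4 events. Taken literally, 5.3 and 9.13 allow 125 mg after the first such event and nothing after the second, so a patient managed under them would never reach the 100 mg or 75 mg level for related marrow toxicity.

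**Later-cycle dose.** Dose per course = daily dose x 21 days.
- 125 x 21 = 2,625 mg
- 100 x 21 = 2,100 mg
- Difference = 525 mg, and 525 / 2,100 = 25%

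From 125 mg the result is 100 mg whether the table's -1 means one step down or the level Table 8.1 labels -1. For a patient already at 100 mg, the first meaning gives 75 x 21 = 1,575 mg and the second leaves 2,100 mg.

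**Restart threshold.** In Table 8.2, Grade 2 is ANC 1.0 to below 1.5, or platelets 50 to below 75 (x 10^9/L). A patient who has recovered only to that range restarts under 5.3 and Table 8.3 and waits under 9.13.

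**Precedence.** Neither 5.3 nor 9.13 refers to 8.4 or Table 8.3. Section 9.10 sends the reader to Section 8.1 for the hematologic limits, but 8.1 contains none.

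**The case against.** The best defence is that a specific rule outranks a general one. Section 8.4 says the schedule holds unless adverse events call for its dose modifications, and it ties Table 8.1 to marrow toxicity. The pointer in 9.10, although misnumbered, looks back to Section 8. This is good evidence of intent and supports the direction of the fix. It does not settle the text: 9.13 includes hematological events in its heading, and the exceptions in both sections omit them.

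The practical safeguards are also real. The trial has one institution and at most 25 patients. The Sponsor-Investigator must approve dose adjustments, and 5.4 leaves removal for adverse events to the investigator's judgment. These limit inconsistent handling. They name who decides, not which rule applies.

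Three stronger readings are tempting, and the documents do not support them.
- A reader might infer that the re-escalation sentence flatly contradicts the permanent reductions. It is permissive and general, and one reduction in Table 8.3 (the second episode within a cycle) is not labelled permanent. The sentence can be read coherently as covering that one. It needs a limiting clause, but it is not the main conflict.
- A reader might infer that neutropenic sepsis immediately produces different restart doses. The permanent reduction sits in the subsequent-cycles column. A restart in the same cycle after a first episode is at 125 mg under every provision.
- A reader might infer that Table 8.3 lowers the dose at every repeat event. It does so only under its named triggers.

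**Conclusion.** The conflict stands on three counts:
1. **Repeat Grade 3-4 marrow event:** removal under 5.3 and 9.13, continued treatment under Table 8.3.
2. **Later cycles after febrile neutropenia, neutropenic sepsis or a missed cycle:** 2,100 mg against 2,625 mg per course, 25% more.
3. **Restart threshold:** Grade 2 or less against Grade 1 or less.

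It should be fixed, because these are safety instructions for the expected toxicity and they cannot all be followed.

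The conclusion rests on the events being judged drug-related. It also rests on the available text: part of 8.4, ahead of the sentence on 75 mg intolerance, was not available, so a precedence statement there cannot be excluded.

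The number of patients affected cannot be estimated. The 42% neutropenia in 9.10 pools doses of 25 to 225 mg and two schedules, and is not a Grade 3-4 rate at 125 mg. For the same reason, a reader might infer that the conflict distorts the time-to-progression result, through early removals falling outside the set defined in 11.1 and being replaced. The documents give no frequency for this, and 11.1 also says efficacy endpoints will be estimated for all subjects. That effect is possible but not shown.

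**What to change.** One amendment can cover all of it:
- **5.3 and 9.13:** state that Table 8.3 governs marrow toxicity for restart threshold, restart dose and handling of a second event. State that the initial-dose restart and second-event removal rules apply to non-hematological toxicity.
- **8.4:** exclude reductions designated permanent in Table 8.3 from the re-escalation sentence, and require Sponsor-Investigator approval there too.
- **9.10:** point to 8.4 and Table 8.3 instead of Section 8.1.

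Table 8.3 is the better rule to keep because it is marrow-specific and graded. Section 9.10 also reports that the cytopenias were reversible, were not cumulative and seldom led to stopping. If the sponsor prefers removal at a second event, Tables 8.1 and 8.3 must be rewritten instead.

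The cost is a few sentences, with no added visits or patients. There are two downsides. Patients with a repeat marrow event stay on treatment, in most triggered cases at a reduced dose, instead of stopping; the rule that ends treatment when 75 mg is not tolerated limits this. Patients with a permanent reduction cannot return to full dose.

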**The Sponsor-Investigator, [name], must approve dose adjustments.**

## 9.0 Safety Measurements

### 9.1 Definitions of Adverse Event

Adverse Event (AE) is any untoward medical occurrence in a patient or trial subject administered a drug or biologic (medicinal) product or using a medical device; the event does not necessarily have a causal relationship with that treatment or usage.

#### **AEs include the following:**

- All suspected adverse medication reactions
- All reactions from medication, overdose, abuse, withdrawal, sensitivity, or toxicity
- Apparently unrelated illnesses, including the worsening of a preexisting illness (see Preexisting Conditions below).
- Injury or accidents. Note that if a medical condition is known to have caused the injury or accident (e.g., a fall secondary to dizziness), the medical condition (dizziness) and the accident (fall) should be reported as two separate adverse events. The outcome of the accident (e.g., hip fracture secondary to the fall) should be recorded under Comments.
- Abnormalities in physiological testing or physical examination (findings that require clinical intervention or further investigation beyond ordering a repeat [confirmatory] test).
- Laboratory abnormalities that require clinical intervention or further investigation (beyond ordering a repeat [confirmatory] test) unless they are associated with an already reported clinical event. Laboratory abnormalities associated with a clinical event (e.g., elevated liver enzymes in a patient with jaundice) should be described under Comments on the report of the clinical event rather than listed as a separate adverse event.

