## **9.3 Procedures**

Diagnostic and therapeutic non-invasive and invasive procedures, such as surgery, should not be reported as adverse events. However, the medical condition for which the procedure was performed should be reported if it meets the definition of an adverse event. For example, an acute appendicitis that begins during the adverse event reporting period should be reported as the adverse event and the resulting appendectomy noted under comments.

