## **9.5 Seriousness (Gravity) of Adverse Event**

Each adverse event is to be classified by the investigator as SERIOUS (including life-threatening) or NONSERIOUS. This classification of the gravity of the event determines the reporting procedures to be followed.

An adverse event that meets one or more of the following criteria/outcomes is classified as **serious**:

- Death
- Life-threatening (i.e., immediate risk of death)
- Inpatient hospitalization, emergency room visit for a period > 24 hours or prolongation of existing hospitalization
- Persistent or significant disability/incapacity
- Congenital anomaly/birth defect
- Other significant medical hazard. An important medical event that may not result in death, threaten life or require hospitalization may be considered a SAE when, based on appropriate medical judgment, it may jeopardize the subject and may require medical or surgical intervention to prevent one of the outcomes listed above. Examples of such

medical events include allergic bronchospasm, requiring intensive treatment in an emergency room or at home, or convulsions that do not result in inpatient hospitalization.

A **nonserious** event is one that does not meet the criteria described for a serious or life-threatening event. Hospitalization for either elective surgery related to a pre-existing condition (without increase in severity or frequency) or routine clinical procedures that are not the result of an adverse event need not be considered as an AE and therefore are not a SAE. A routine clinical procedure is a procedure occurring during the study period that does not interfere with the study product administration or any of the ongoing protocol specific procedures. If anything untoward is reported during an elective procedure, that occurrence must be reported as an AE or SAE, according to the usual criteria.

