### **9.9 Recording Instructions**

On the adverse event case report forms, the investigator will use the NCI Common Toxicity Criteria (CTC) version 4.0 ([http:// ctep.info.nih.gov/ CTC3/default.htm](http://ctep.info.nih.gov/CTC3/default.htm)) to describe the maximum intensity of the adverse event. The investigator will also be asked to assess the possible relationship between the adverse event and the investigational medication as well as any concomitant medications.

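### The worked example in section 9.1 records an injury from an accident under Comments, so the injury can be left without its own adverse event term, grade and attribution

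*Combined protocol and SAP*

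**What the plan says.** Section 9.1 defines the unit of safety reporting broadly: "Adverse Event (AE) is any untoward medical occurrence in a patient or trial subject administered a drug or biologic (medicinal) product". The list that follows has a bullet headed "Injury or accidents". Its note covers an accident brought about by a known medical condition and says that "the medical condition (dizziness) and the accident (fall) should be reported as two separate adverse events". The next sentence deals with the injury: "The outcome of the accident (e.g., hip fracture secondary to the fall) should be recorded under Comments".

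Other sections fix what happens to an entry once it is an adverse event:

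- Section 9.7 has the investigator attribute each adverse event.
- The Recording Instructions (the second section numbered 9.9) use the CTCAE scale "to describe the maximum intensity of the adverse event".
- Section 2.2 lists safety and tolerability as an endpoint, with adverse events as a component; it is a secondary objective in 2.12.
- Section 11.2 plans descriptive statistics and nothing further.

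Section 9.3 has a related rule. A procedure is not itself an adverse event, but "the medical condition for which the procedure was performed should be reported if it meets the definition of an adverse event", with the procedure noted in the comments.

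**The concern.** The example has three elements: a condition, an accident and an injury. The first two become adverse events. The third, which is usually the clinically important one, becomes comment text. Grade and attribution belong to adverse events, so comment text receives neither, and section 11.2 has no step for coding or counting it.

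Two things are at stake. The first is the content of the safety summary: a fracture may be represented by a fall and a dizzy spell, without appearing under its own name. The second is consistency. Two members of staff could record the same fracture differently, each with support in the protocol, one relying on the example and the other on the general definition. In a trial capped at 25 patients, the summary then depends partly on who filled in the form.

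**Working it through.** The documents state no figure on this point and there is none to reproduce. The check is a comparison of the texts.

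**1. Does the example keep the injury off the adverse event list?** It names what is reported (condition and accident, as two events) and places the injury elsewhere. The last bullet of the same list shows how 9.1 uses Comments: a laboratory abnormality tied to a clinical event is described there instead of being listed separately. That supports reading Comments as an alternative to an adverse event entry. The sentence does not, however, say that the injury goes there exclusively.

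**2. What does the injury lose if it is only comment text?**

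| Element of the example | Adverse event term | CTCAE grade (Recording Instructions) | Attribution (9.7) | In the descriptive summary (11.2) |
|---|---|---|---|---|
| Dizziness | yes | yes | yes | yes |
| Fall | yes | yes | yes | yes |
| Hip fracture | none of its own | none of its own | none of its own | no stated route |

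**3. Is that consistent with the rest of section 9?**

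- *General definition, 9.1.* A hip fracture in a treated patient meets it.
- *Same bullet.* The heading names injury as well as accidents, so injury is a listed adverse event that the example then treats as a comment.
- *Section 9.3.* If the fracture is repaired surgically, the condition behind the operation is to be reported when it meets the definition. The same fracture is then an adverse event under 9.3 and a comment under 9.1.
- *Direction of the rules.* In 9.3 and in the laboratory bullet, the clinical condition stays as the adverse event and the secondary item (procedure or laboratory value) goes to Comments. In the accident example it is the clinical injury that goes to Comments.

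**4. What is retained?** The fall keeps its own entry, described at maximum intensity and attributed. Under 9.5 it is serious if, for example, it leads to "Inpatient hospitalization, emergency room visit for a period > 24 hours or prolongation of existing hospitalization".

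**5. How large is the effect?** The documents give no rate of falls or fractures, so the number of patients affected cannot be derived and zero is possible. For scale only: at the maximum accrual of 25, one affected patient changes the incidence of that injury term by 1/25 = 4 percentage points. The same is true of any single event in a trial of this size, and it says nothing about how often the case will arise.

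**The case against.** The best defence is that the protocol, read as a whole, already makes the injury reportable. Injury is in the bullet heading, the definition covers it, and 9.3 captures a fracture that needs surgery. The first bullet of the list also makes every suspected drug reaction an adverse event, so an injury the investigator suspects is drug-related has its own route to an entry and an attribution. On this view the sentence is a convention for linked terms, and whether to split or group such terms is partly preference.

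Much of this stands. It shows that the fault is an inconsistency and not a clear exclusion. It does not remove the fault: a specific worked example is what a form or a coordinator is likely to follow, and it points the other way.

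Oversight is also less exposed than a reader might suppose. The table in 9.8 sorts reports by grade and attribution, but the text above it, repeated in section 14.0, sends serious adverse events to the IRB and the monitoring committee within 48 hours without a grade or attribution condition. The medical monitor reviews all adverse events. A fall that puts a patient in hospital would reach both.

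A reader might go further and infer that traumatic bleeds are hidden in patients whom section 8.4 describes in these terms: "Due to baseline coagulopathy and tendency to have bleeding events due to underlying liver disease". The documents do not support that. The only example is a fracture, no text sends bleeds to Comments, and a bleed suspected to be drug-related is reportable under the first bullet. The phrase in 8.4 explains why dose modification should not rest on hemoglobin and has nothing to do with accidents. Nor does the plan contain a bleeding table, a table of Grade 3 or higher events, or confidence limits for adverse events that could be shown to be distorted.

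**Conclusion.** The point holds as an internal inconsistency in adverse event recording. Followed literally, the example in 9.1 can leave an injury from an accident without its own term, grade and attribution, and so outside the descriptive summary. This conflicts with the definition in 9.1, with the heading of the same bullet and with 9.3.

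It is minor. It touches only secondary, descriptive safety reporting; time to progression, sample size and error rates are unaffected. The accident itself stays on record with a grade, an attribution and, where 9.5 is met, serious status. The number of patients affected is unknown and may be zero.

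The conclusion assumes that site staff follow the worked example and that comment text is not coded for analysis; the documents state no such coding. They also do not say whether the Comments sentence applies to accidents with no known medical cause, so its reach could be narrower or wider than the example.

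It would be too strong to say that traumatic fractures are excluded from the safety data. The text contains no such exclusion, and other parts of section 9 support reporting them.

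**What to change.** Replace the Comments sentence in 9.1 with: *Each injury resulting from the accident (e.g., hip fracture) is reported as a separate adverse event with its own grade, seriousness and attribution, linked to the accident and to any causal condition.* Keep Comments for the narrative that ties the entries together, and align the case report form instruction. The wording should apply whether or not a medical condition caused the accident, which also settles the question of reach.

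The cost is one sentence, the matching form instruction and a few more linked entries per accident. Because one episode can then yield three events, summaries under 11.2 should give the number of patients as well as the number of events, so that linked entries do not inflate the picture. No dose, schedule or clinical rule is affected.
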